5.1. Primary analysis

The change in the primary outcome (KOOS-Pain) from baseline to primary endpoint (12 weeks) will be calculated for both groups, and a mixed linear model will be used to examine if there is a systematic difference between the two intervention groups.

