2.2. Sample size calculation

The estimated number of participants in the study are based on the primary outcome variable, KOOS-Pain subscale⁴⁹, with the assumption that a change of 10 KOOS points may be considered of clinical relevance^{49,50} as well as assuming a standard deviation (SD) averaging 15 KOOS points^{11,50}. Assuming a statistical power of 80 %, a significance level of 0.05 and an expected within-group change in KOOS of 10 points magnitude with 12 weeks training (primary endpoint), was calculated to require 37 participants. To compensate for potential dropouts, a total of 90 participants are planned to be included in the study, divided equally and randomly into two intervention groups (45 participants in each group).

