3.2. Secondary outcomes

Secondary outcome variables at functional level includes:

- 4x10 m maximal horizontal fast-paced walking^{51,52}
- 30-s chair-stand test⁵¹⁻⁵⁴
- Stair Climb test (12 steps)^{51,55-58}
- Pain Pressure Threshold on affected and non-affected side⁵⁹⁻⁶⁴
- Total KOOS score^{49,50}
- Oxford Knee Score^{49,65}

Secondary outcome parameters related to mechanical muscle function will be obtained as well, including:

- Maximal isometric knee extensor (KE) strength (KinCom, isokinetic dynamometer)⁶⁶⁻⁶⁸
- KE Rapid force capacity (Rate of Force Development, RFD) (KinCom, isokinetic dynamometer)^{66,68,69}
- Maximal leg muscle power (Nottingham Power Rig)^{11,69-71}
- Lower limb muscle mass (Ultrasonography)⁷²⁻⁷⁹
- Muscle biopsies will be obtained from the thigh muscle (vastus lateralis) for evaluation of myocellular properties (myofiber area, vascularization, muscular satellite cells, myonuclei content)^{40,80-84}

Testing will take place before the intervention period, after 8 weeks of training and at the end of the intervention (12 weeks) except for the muscle biopsies which will be obtained before the intervention period and at 12 weeks (primary endpoint). Moreover, patient-reported questionnaires and functional performance will be assessed 6 months after the intervention period.

4. Inclusion and exclusion criteria

All people with symptoms of knee-OA or patients diagnosed with knee-OA are eligible.

To be included in the study, participants must meet the following inclusion criteria:

- All participants must meet the American College of Rheumatology (ACR) criteria for OA⁸⁵
- Visible OA on X-ray pictures (Kellgren & Lawrence grade 2-3)⁸⁶
- Pain and functional limited for a minimum of 3 months
- Be able to voluntarily (i.e. unassisted) perform a 90 degrees flexion in the knee while standing
- Be able to perform loaded machine exercise (knee extension) planned for the BFR training
- Be able to understand written and spoken danish
- Be able to complete the intervention period without extensive time away

Individuals will be excluded if meeting these exclusion criteria:

- Kellgren & Lawrence grade 1 and 4⁸⁶
- Bilateral OA-symptoms
- Prior knee- or hip alloplasty
- Glucocorticosteroid injection in the knee within the last 6 months
- Inflammatory arthritis
- Known neurotic disease such as multiple sclerosis or peripheral neuropathy
- Prior myocardial infarct or apoplexy, or chest pain during physical activity

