5.2. Secondary analyses

For all secondary outcomes, including the primary outcome, assessed at multiple time points (more than two) will be analysed using a mixed linear model approach. Secondary outcomes assessed at baseline and at one more time point will be analysed as described for the primary outcome above.

Explorative analysis will be conducted. The primary outcome will be correlated to the various secondary outcomes.

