5.3. Intention-to-treat (ITT) analysis

Statistical ITT analysis will include all subjects who are randomized to the intervention procedures.

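### The primary KOOS-Pain comparison (SAP 5.1) states no baseline adjustment; adding it would gain precision from data already collected

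*SAP*

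**What the plan says.** SAP 5.1 is one sentence in two parts. The first part sets the quantity to be compared: "The change in the primary outcome (KOOS-Pain) from baseline to primary endpoint (12 weeks) will be calculated for both groups". The second part gives the method: "a mixed linear model will be used to examine if there is a systematic difference between the two intervention groups". It does not state the response variable, the visits included, the covariates, the fixed or random effects, or how the baseline means are treated.

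SAP 5.2 bears on how 5.1 is read:
- For one-follow-up outcomes it says "Secondary outcomes assessed at baseline and at one more time point will be analysed as described for the primary outcome above". This makes 5.1 the template for a two-time-point analysis.
- It places the multi-visit model of KOOS-Pain among the secondary analyses, in the words "including the primary outcome, assessed at multiple time points (more than two) will be analysed using a mixed linear model approach". It does not name the contrast to be taken from that model.

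SAP 5.3 says "Statistical ITT analysis will include all subjects who are randomized to the intervention procedures". SAP 2.3 places randomisation after the baseline assessment, and SAP 3.2 schedules tests at baseline, week 8 and week 12, with "patient-reported questionnaires and functional performance will be assessed 6 months after the intervention period". SAP 2.2 plans 45 participants per group, "assuming a standard deviation (SD) averaging 15 KOOS points", without saying whether this is the SD of a score or of a change. The protocol has a power section but no analysis model.

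**The concern.** The baseline KOOS-Pain score is measured in everyone before randomisation, so it is a legitimate covariate for the primary comparison. The text commits to a change from baseline and to no adjustment.

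Naming a mixed model does not supply the adjustment. There are two natural ways to follow 5.1:
- (a) take the change as the response;
- (b) take the baseline and week-12 scores as repeated measures, with a free baseline mean in each group.

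With complete data both give the same estimate, the difference in mean change. Precision on the primary endpoint is therefore left unused. Depending on what the SD of 15 describes, and on r, the unadjusted test may fall short of the 80% power the trial was sized for. With the model unstated, the choice between an adjusted and an unadjusted primary result is also left to the analysis stage.

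**Working it through.** **Inputs from the documents (SAP 2.2):** difference 10 points, SD 15, power 80%, significance level 0.05, 37 required, 45 planned per group.

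**Assumed, not in the documents:** a two-sided test; the same SD at baseline and week 12; the correlation r between them, shown from 0.3 to 0.9; 37 analysed per arm.

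**The plan's own figure.** A two-sample, two-sided t-test with difference 10 and SD 15 needs 36.3, rounded up to 37 per arm. So 37 reproduces as a per-arm number for a between-group comparison, although SAP 2.2 words the 10 points as a within-group change. A paired calculation with SD of change 15 needs only 20. Going from 37 to 45 per arm allows for 1 − 37/45 = 17.8% dropout. No gain from baseline adjustment is built in.

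**Variance (SD = score SD).**
- Difference in change: 2·SD²·(1 − r) per participant.
- Baseline-adjusted: SD²·(1 − r²) per participant.
- Ratio: (1 − r²) / [2(1 − r)] = (1 + r)/2, that is 0.65, 0.75, 0.85 and 0.95 at r = 0.3, 0.5, 0.7 and 0.9.

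Simulation at 37 per arm gave ratios of 0.66, 0.77, 0.86 and 0.97, with no bias. In simulated two-visit data, a mixed model with free baseline means reproduced the change-score estimate to rounding error. A common-baseline model correlated above 0.99 with ANCOVA.

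**Worked example, r = 0.5, 37 per arm, score SD 15.**
- Unadjusted: SD of change 15·√(2·0.5) = 15.00; SE = 15.00·√(2/37) = 3.49; 95% CI half-width 6.95.
- Adjusted: residual SD 15·√0.75 = 12.99; SE = 12.99·√(2/37) = 3.02; half-width 6.02.

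**Power for 10 points** (noncentral t; df 2n − 2 unadjusted, 2n − 3 adjusted), unadjusted → adjusted:

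| r | n = 37, 15 is score SD | n = 37, 15 is SD of change | n = 45, score SD | n = 45, SD of change |
|---|---|---|---|---|
| 0.3 | 66.7 → 84.3% | 80.8 → 93.9% | 75.3 → 90.6% | 87.9 → 97.2% |
| 0.5 | 80.8 → 90.4% | 80.8 → 90.4% | 87.9 → 95.1% | 87.9 → 95.1% |
| 0.7 | 95.5 → 97.7% | 80.8 → 86.6% | 98.1 → 99.2% | 87.9 → 92.4% |
| 0.9 | both near 100% | 80.8 → 82.7% | both near 100% | 87.9 → 89.4% |

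The CI half-width at 37 per arm with score SD 15 goes from 8.23 to 6.63 points (r = 0.3), 6.95 to 6.02 (0.5), 5.39 to 4.97 (0.7) and 3.11 to 3.03 (0.9). Allowing for chance baseline imbalance multiplies the adjusted variance by about 1 + 1/70. That widens these intervals by at most 0.05 points and lowers adjusted power by at most about 0.6 percentage points. On this allowance adjustment stops paying only above r of about 0.97.

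**Where 80% is lost.** On the score-SD reading, unadjusted power is below 80% when r is under 0.49 (37 per arm) or 0.38 (45 per arm). Adjusted power at 37 per arm is lowest at r = 0 on the score-SD reading and as r approaches 1 on the SD-of-change reading. It is 80.7% in both cases, or 80.2% after the imbalance allowance.

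**Equivalent sample size.** An adjusted analysis of 45 per arm is as precise as an unadjusted one of 45/0.65 = 69, 45/0.75 = 60, 45/0.85 = 53 or 45/0.95 = 47 per arm.

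**With dropout** (assumed 37 completers and 8 dropouts per arm, score SD 15; r = 0.3 / 0.5 / 0.7, with week 8 to 12 correlation 0.6 / 0.7 / 0.8), SE of the week-12 contrast:

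| Model | SE |
|---|---|
| (a) change as response | 4.13 / 3.49 / 2.70 |
| (b) free baseline means | 4.00 / 3.41 / 2.67 |
| Common baseline, no week 8 | 3.33 / 3.02 / 2.49 |
| Common baseline, week 8 seen in 4 of 8 dropouts | 3.28 / 2.97 / 2.45 |
| Common baseline, week 8 seen in all dropouts | 3.23 / 2.92 / 2.41 |

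Nearly all the gain comes from the baseline. Week 8 adds nothing with complete data and 1.5% to 3.3% of the SE here.

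**The case against.** The strongest reply is that nothing in SAP 5.1 is invalid. The difference in change is unbiased under randomisation. Because SAP 2.2 ties the 10 points to a change, 15 may well be the SD of change. Unadjusted power is then 80.8% at 37 per arm and 87.9% at 45, whatever r is. The gain also shrinks as r rises, to 5% of the variance at r = 0.9. All of this stands, and it makes the matter one of precision, not of error.

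A second reply is that (a) and (b) are not the only readings. A mixed model has little purpose with one change value per person, so 5.1 might mean the week-12 contrast from a model that includes week 8. That is possible, and it weakens any claim that week 8 is ignored. It does not supply the adjustment: with complete data, a three-visit model with free baseline means still gives the difference in change.

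A third reply is that a single covariate would do, and that a three-visit model is more than the problem needs. For precision alone this is largely right, as the last table shows. Week 8 also protects against dropout that depends on the week-8 score, but that would bias the comparison only if the dropout process differed between arms, and the documents give no sign of this. The three-visit form is therefore a preference; the baseline adjustment is the substance.

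**Conclusion.** The point holds. SAP 5.1 commits to a change from baseline and to no baseline adjustment, and no other section adds one. The planned comparison is valid but gives up precision: a variance cut of 35% at r = 0.3, falling to 5% at r = 0.9.

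A shortfall below 80% power arises only if 15 is the score SD and r is below 0.49 (37 analysed per arm) or 0.38 (45 per arm). The documents settle neither. Adjustment keeps power at about 80% or more for r from 0 upward under either reading of the SD, so it removes the dependence on facts the plan does not state.

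These sizes rest on equal SDs at the two visits, an assumed r, a two-sided test and 37 read as a per-arm number. The change should be made; leaving it out would not invalidate the trial.

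**What to change.** In SAP 5.1, define one primary analysis: a mixed model of KOOS-Pain scores at baseline, week 8 and week 12 in all randomised participants, with a common baseline mean across groups, visit and group-by-visit terms, and an unstructured within-participant covariance. The primary test is the group contrast at week 12, under a stated missing-at-random assumption. If a simpler model is preferred, ANCOVA of the week-12 score on group and baseline score captures nearly all the gain.

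In SAP 5.2:
- use baseline-adjusted ANCOVA for outcomes with one follow-up value, such as the biopsy measures;
- state that the secondary multi-visit KOOS-Pain results (week 8 and 6 months) do not provide a second week-12 test.

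Add a rule for any missing baseline score. The cost is a few lines of text and about one degree of freedom. No participants, visits or measurements are added, and SPSS, the package the SAP names, can fit the model.

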5.2. Secondary analyses

For all secondary outcomes, including the primary outcome, assessed at multiple time points (more than two) will be analysed using a mixed linear model approach. Secondary outcomes assessed at baseline and at one more time point will be analysed as described for the primary outcome above.

Explorative analysis will be conducted. The primary outcome will be correlated to the various secondary outcomes.

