3.1. Primary outcome

Primary outcome variable is KOOS (Knee injury and Osteoarthritis Outcome Score) Pain subscale. KOOS is an instrument to assess the patient's opinion about their knee

and associated problems. KOOS consists of 5 subscales; Pain, Symptoms, Function in daily living (ADL), Function in sport and recreation (Sport/Rec) and knee related quality of life (QOL).

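### The exploratory correlations pair KOOS-Pain with Total KOOS, a score that on its ordinary reading contains Pain, so that one coefficient is inflated by construction

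*SAP*

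**What the plan says.** Four statements in the SAP bear on this.

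- Section 3.1 sets the primary outcome: "Primary outcome variable is KOOS (Knee injury and Osteoarthritis Outcome Score) Pain subscale".
- The same section describes the instrument: "KOOS consists of 5 subscales; Pain, Symptoms, Function in daily living (ADL), Function in sport and recreation (Sport/Rec) and knee related quality of life (QOL". Pain is therefore one of its five components.
- Section 3.2 lists "Total KOOS score" among the secondary outcomes, without a scoring rule or weighting.
- Section 5.2 announces that "Explorative analysis will be conducted" and then that "The primary outcome will be correlated to the various secondary outcomes".

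No section excludes Total KOOS from these correlations or plans a version of the total without Pain. Section 5.2 also does not say whether levels or changes are to be correlated. The protocol does not help: under Outcome measures it names KOOS as primary without choosing a subscale, and it plans no correlations.

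**The concern.** When a score is correlated with a total that contains it, part of the coefficient is the score correlated with itself. A Pain-Total KOOS coefficient would therefore overstate how closely pain tracks the other KOOS domains.

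It would also be reported in the same set as coefficients for outcomes that share no items with KOOS-Pain, such as chair stand, knee extensor strength and leg power. The coefficients would not be comparable, and Total KOOS could look like the strongest correlate of pain for a purely structural reason.

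**Working it through.** The documents give no figure for this correlation, so there is nothing of the plan's own to reproduce. The check has three parts.

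**1. Direction, without outside figures.** Let P be Pain, R the (weighted) rest of the total, a = SD(P)/SD(R), with any weight on Pain absorbed into a, and ρ = corr(P, R). Then

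corr(P, P + R) = (a + ρ) / √(a² + 1 + 2aρ).

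The expression under the root equals (a + ρ)² + (1 − ρ²). Writing u = a + ρ, the correlation is u / √(u² + 1 − ρ²), which increases with u and equals ρ when a = 0. For every a > 0 and |ρ| < 1 it therefore exceeds ρ. A numerical grid (a from 0.01 to 5, ρ from −0.99 to 0.99) agrees: the smallest difference was 0.0002, above zero. The argument applies equally to levels and to changes, because the change in a total contains the change in Pain.

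**2. Size, under stated assumptions.** The documents give no correlations between subscales, so I assume that Total KOOS is the equal-weight mean of five subscales with equal SD and a common correlation r. Then

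- Pain with Total: √((1 + 4r)/5)
- Pain with the mean of the other four: 2r / √(1 + 3r)

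At r = 0.5 these are √(3/5) = 0.775 and 1/√2.5 = 0.632, a difference of 0.142 before rounding of the two terms.

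| Assumed r | Pain with Total | Pain with other four | Excess |
|---|---|---|---|
| 0 | 0.447 | 0.000 | 0.447 |
| 0.3 | 0.663 | 0.435 | 0.228 |
| 0.5 | 0.775 | 0.632 | 0.142 |
| 0.7 | 0.872 | 0.795 | 0.077 |
| 0.9 | 0.959 | 0.936 | 0.023 |

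Now let each non-pain subscale have an SD of k times the Pain SD. The correlation of Pain with the other four is unchanged, and the correlation with the total becomes

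(1 + 4kr) / √(1 + 8kr + k²(4 + 12r)).

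For k = 0.75 and r = 0.5 this is 2.5/√9.625 = 0.806, an excess of 0.173. For k = 1.5 and r = 0.5 it is 4/√29.5 = 0.736, an excess of 0.104. At r = 0.9 the excess is 0.028 for k = 0.75 and 0.017 for k = 1.5. Because k multiplies each non-pain score, unequal weights on Pain relative to the other four act in the same way.

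**3. Illustration at the planned size.** SAP 2.2 states that "a total of 90 participants are planned to be included in the study". I used n = 90, an SD of 15 points for every subscale (the SAP gives that figure for KOOS-Pain; using it for the others is an assumption) and 4,000 simulated trials.

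- With unrelated subscales (r = 0), the Pain-Total correlation averaged 0.45 and passed the nominal 5% threshold (|r| > 0.207) in 99.5% of runs. Pain with the other four averaged 0.00 and passed in 4.8%.
- With r = 0.5 the averages were 0.773 and 0.631, and both passed in every run.

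The case r = 0 is a limit, not an expectation for subscales of one questionnaire. It shows only that a significant Pain-Total coefficient is not in itself evidence that pain is related to the other domains.

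**The case against.** The premise needs two readings that the SAP does not spell out. Total KOOS is undefined and could mean the complete questionnaire reported subscale by subscale, in which case there is no aggregate that contains Pain. Section 5.2 also speaks of various secondary outcomes, while elsewhere in the same section it writes of all of them, so this pair may never be computed. Both readings are possible. Neither is stated, and on the ordinary meaning of a total score the overlap exists.

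The harm also depends on use. The SAP attaches no hypothesis, ranking or decision to any correlation, and a Pain-Total coefficient is a valid estimate of what it names. It misleads only when read as pain against the other domains, or when compared with the rest of the set. That stands, and it is why the point is minor.

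The size is not tied to this trial either: at correlations of 0.7 to 0.9 the excess is only 0.077 to 0.023 with equal SDs. That stands too, and the documents cannot show which part of the range applies.

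Finally, the correlation analysis leaves the coefficient, time point and scale open for every pair. That is a wider gap, but filling it would not remove this overlap.

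**Conclusion.** The concern holds. As written, the plan allows a part-whole correlation between KOOS-Pain and Total KOOS, and its upward bias relative to Pain with the remaining subscales is certain for any positively weighted total that contains Pain and whose remainder is not perfectly correlated with it. That Total KOOS contains Pain is an inference from SAP 3.1, because the SAP does not define the score.

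Under equal weights and SDs the excess runs from 0.447 (unrelated subscales) to 0.023 (correlation 0.9), with 0.142 at a correlation of 0.5. Those correlations are assumptions.

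The consequence is limited to one exploratory coefficient. The primary between-group comparison in SAP 5.1, the sample size in SAP 2.2 and the other correlations are not affected. This is a worthwhile small improvement, not a condition for the trial's validity.

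**What to change.** Add one sentence to SAP 5.2, for example: *Scores that contain KOOS-Pain (Total KOOS) are left out of the correlation set; KOOS-Pain is correlated instead with the Symptoms, ADL, Sport/Rec and QOL subscales, either singly or as a total without Pain.*

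Total KOOS can stay as a secondary outcome in SAP 3.2. A short scoring rule there would also settle what the total contains.

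The cost is small. The subscales come from the questionnaire already administered, so no data are added. The four non-pain subscales are not listed separately as secondary outcomes, so using them singly means up to four exploratory correlations in place of one. A single total without Pain keeps it at one, but that derived score would need its own one-line definition.

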5.3. Intention-to-treat (ITT) analysis

Statistical ITT analysis will include all subjects who are randomized to the intervention procedures.

